## 1. LIST OF ABBREVIATIONS

AAA	Abdominal aortic aneurysm
ADE	Adverse Device Effect
AE	Adverse Event
CER	Clinical Evaluation Report
CTO	Chronic Total Occlusion
IAA	Iliac Artery Aneurysm
IC	Intermittent Claudication
ISO	International Organization for Standardization
MEDDEV	MEDical DEvice (i.e. European Commission's official guidance for medical devices)
PMCF	Post-Market Clinical Follow-up
CLTI	Chronic Limb Threatening Ischemia

PROTOCOL	2020-PMC-01
TITLE:	Safety and Performance of POLYMAILLE® C vascular prosthesis
EFFECTIVE DATE:	15 January 2021

## 2. SYNOPSIS

Title:	A Retrospective, Observational, Multicentre Study to Collect Clinical Safety and Performance data on POLYMAILLE® C vascular prosthesis
Study Population:	Subjects who did receive POLYMAILLE® C at least one year ago for replacement or bypass of arteries. 2 main sub-populations will be studied depending on location of surgery (abdominal and peripheral), but data will be collected for all subjects who did receive POLYMAILLE® C.
Study Design:	Multi-center retrospective case series
Study Type:	PMCF
Number of subjects:	Data from a minimum of 200 subjects will be evaluated. A minimum of 100 subjects will be evaluated for each main location of surgery (abdominal and peripheral).
Follow-up	At least 1 year follow-up after surgery until a maximum of 5 years.
Study Product:	POLYMAILLE® C vascular prosthesis
Intended use:	POLYMAILLE® C vascular prostheses are indicated for replacement or bypass of arteries presenting aneurysm or obliterative arterial disease. Their indication is restricted to abdominal and peripheral surgery not crossing the knee flexion crease.
Objectives:	Describe safety and performance of POLYMAILLE® C
Performance primary endpoint:	Primary patency rate at 1 year after surgery using POLYMAILLE® C
Safety primary endpoint:	Mortality rate at 30 days after surgery using POLYMAILLE® C
Performance secondary endpoints:	
 
• Procedural success rate
 
• Primary patency rate at 30 days and 6 months after surgery using POLYMAILLE® C
 
• Primary assisted patency rate at 30 days, 6 months and 1 year after surgery using POLYMAILLE® C
 
• Secondary patency rate at 30 days, 6 months and 1 year after surgery using POLYMAILLE® C
 
• Device failure during procedure or at discharge, at 30 days, 6 months and 1 year after surgery using POLYMAILLE® C
 

PROTOCOL	2020-PMC-01
TITLE:	Safety and Performance of POLYMAILLE® C vascular prosthesis
EFFECTIVE DATE:	15 January 2021

Safety secondary endpoints	
 
• Mortality rate during procedure or at discharge, at 6 months and 1 year after surgery using POLYMAILLE® C
 
• Limb salvage rate at 30 days, 6 months and 1 year after surgery using POLYMAILLE® C
 
• Adverse event during procedure or at discharge, at 30 days, 6 months and 1 year after surgery using POLYMAILLE® C
 

Exploratory endpoints	
 
- After 1 year until the end of follow-up (5 years) using POLYMAILLE® C: 
 
○ Primary patency
 
○ Primary assisted patency
 
○ Secondary patency
 
○ Device failure
 
○ Mortality
 
○ Limb salvage
 
○ Adverse events
 
 
 
- Identify possible systematic misuse or off-label use of POLYMAILLE® C, with a view to verifying that the intended clinical purpose is correct.
 

Inclusion criteria	Subjects who did receive POLYMAILLE® C at least one year ago for replacement or bypass of pathological arteries.
Exclusion criteria	Patients who have objected to the collect of their data
Duration of the data collect:	6 months from first site operational to collect data until data delivery

---

PROTOCOL	2020-PMC-01
TITLE:	Safety and Performance of POLYMAILLE® C vascular prosthesis
EFFECTIVE DATE:	15 January 2021

---

---

**Data to be collected (as far as available)**

- **Identification and demographic data**
  - Patient identification
  - Indication and location of the lesion(s)
  - Patients demographics and risk factors
  - Summary of previous cardiovascular interventions
  - Relevant medications
  - Diagnosis
- **Operative data**
  - Date of procedure
  - Identification data for the prosthesis
  - Information related to the surgical procedure
  - Relevant medication
  - Assessment of prosthesis function and mode of assessment if available
  - Device failure modes and documented adverse operative events
- **Post-operative data (follow-up)**
  - Date of follow-up visits
  - Summary of vascular interventions, including minimally invasive procedures
  - Clinical evaluation
  - Relevant medications
  - Device failure modes and documented adverse events
- **Any documented adverse events data (as far as available)**
  - Type of event, date of occurrence, severity, management, outcome
  - Any Documentation of probable causative factors (e.g. caused by the prosthesis, patient factors, technical factors)

---

---

PROTOCOL	2020-PMC-01
TITLE:	Safety and Performance of POLYMAILLE® C vascular prosthesis
EFFECTIVE DATE:	15 January 2021

---

---

Timepoints of interests	

- During procedure and at discharge (7-14 days)

- 30-days after surgery ('peri-operative')

- 6, 12 months

- After 1 year until the end of follow-up (5 years)

--------------------------------	---

---

### 3. INTRODUCTION.

POLYMAILLE® C devices are CE-marked and were initially introduced in the international market in 2002. Since January 2004, more than 55 000 single devices have been sold across various markets worldwide.

### 4. STUDY DEVICE

#### 4.1. Summary description of the device

The studied device is POLYMAILLE® C (Figure 1), which consists in uniform straight or bifurcated tubular synthetic textile coated vascular grafts.

POLYMAILLE® C vascular grafts are made by knitting of polyethylene terephthalate (PET – polyester) yarns and impregnated with collagen CXE® coating of bovine origin.

CXE® collagen impregnation of the POLYMAILLE® C vascular grafts ensure water permeability of less than 5 ml/cm^2/min at a pressure of 120 mm of mercury (Hg) and allows direct implantation of the prosthesis without the need for pre-clotting.

PROTOCOL	2020-PMC-01
TITLE:	Safety and Performance of POLYMAILLE® C vascular prosthesis
EFFECTIVE DATE:	15 January 2021

Figure 1: Uniform straight and bifurcated POLYMAILLE® C vascular grafts

POLYMAILLE® C vascular grafts are available in different configurations as summarized in the below tables:

**Table 1** – POLYMAILLE® C CE-marked straight references

Reference	Nominal relaxed and pressurized inner diameter (mm)	Minimum usable length (cm)
PMC000640	6	40
PMC000660	6	60
PMC000670	6	70
PMC0006100	6	100
PMC000740	7	40
PMC000760	7	60
PMC000770	7	70
PMC0007100	7	100
PMC000840	8	40
PMC000860	8	60
PMC000870	8	70
PMC0008100	8	100
PMC001040	10	40
PMC001060	10	60
PMC001070	10	70
PMC0010100	10	100
PMC001230	12	30
PMC001240	12	40

PROTOCOL	2020-PMC-01
TITLE:	Safety and Performance of POLYMAILLE® C vascular prosthesis
EFFECTIVE DATE:	15 January 2021

Reference	Nominal relaxed and pressurized inner diameter (mm)	Minimum usable length (cm)
PMC001260	12	60
PMC001270	12	70
PMC001415	14	15
PMC001430	14	30
PMC001440	14	40
PMC001460	14	60
PMC001470	14	70
PMC001615	16	15
PMC001630	16	30
PMC001640	16	40
PMC001815	18	15
PMC001830	18	30
PMC001840	18	40
PMC002015	20	15
PMC002030	20	30
PMC002040	20	40
PMC002215	22	15
PMC002230	22	30
PMC002240	22	40
PMC002415	24	15
PMC002430	24	30
PMC002440	24	40

**Table 2** – POLYMAILLE® C CE-marked bifurcated references

Reference	Main tube nominal relaxed and pressurized inner diameter (mm)	Branches nominal relaxed and pressurized inner diameter (mm)	Minimum usable overall length (cm)
PMC120650	12	6	50
PMC140750	14	7	
PMC160850	16	8	
PMC180950	18	9	
PMC201050	20	10	
PMC221150	22	11	
PMC241250	24	12	

---

PROTOCOL	2020-PMC-01
TITLE:	Safety and Performance of POLYMAILLE® C vascular prosthesis
EFFECTIVE DATE:	15 January 2021

---

## 4.2. Intended purpose and patient population

### 4.2.1. Intended clinical purpose

POLYMAILLE®C vascular prostheses are indicated for replacement or bypass of arteries presenting aneurysm or obliterative arterial disease. Their indication is restricted to abdominal and peripheral surgery not crossing the knee flexion crease.

Abdominal vascular surgery includes abdominal aorto-aortic and/or aorto-iliac and/or aorto-femoral vascular repair, i.e. graft implantation with proximal anastomosis to abdominal aorta (supra and/or infra-renal).

Peripheral vascular surgery includes peripheral arteries repair, i.e. graft implantation with no aortic anastomosis, and/or extra-anatomic vascular repair such as axillo-femoral and/or crossover bypass (femoro-femoral and/or ilio-femoral).

### 4.2.2. Patient population characteristics

Patient population conditions that may indicate abdominal and/or peripheral vascular open surgical repair with implantation of a vascular graft include:

- Peripheral arterial diseases (PAD), characterized by reduced blood flow to the lower extremities, which may be categorized as:
  - Intermittent claudication (IC)
  - Chronic limb-threatening ischemia (CLTI)
  - Acute limb ischemia (ALI)
  - Chronic total occlusion (CTO)
- Arterial aneurysms, characterized by a permanent localized (i.e., focal) dilatation having at least a 50% increase in diameter, which may be categorized by location:
  - Abdominal aortic aneurysms (AAA)
  - Peripheral arterial aneurysms
    - Iliac arterial aneurysms (IAA)
    - Femoral arterial aneurysms (FAA)
    - Popliteal arterial aneurysms (PAA)

#### 4.2.2.1. Peripheral arterial diseases (PAD)

Reported PAD risks factors are:

- History of cardiovascular disease
- Smoking
- Diabetes mellitus
- Hypertension

---

PROTOCOL	2020-PMC-01
TITLE:	Safety and Performance of POLYMAILLE® C vascular prosthesis
EFFECTIVE DATE:	15 January 2021

---

- Dyslipidemia
- Obesity
- Age

Age is the strongest risk factor for PAD. The disease is rare in individuals younger than 40 years, rises in prevalence in the sixth to eighth decades, and may affect 25% or more of individuals 80 years and older.

#### 4.2.2.2. Arterial aneurysms

Reported arterial aneurysms risks factors are:

- advanced age,
- gender,
- smoking,
- family history,
- obesity,
- co-morbidities such as coronary heart disease, diabetes, atherosclerosis.

Prevalence of abdominal aortic aneurysms (AAA) 4 cm or larger is approximately 1% of men between the ages of 55 and 64 years and increases with advancing age by 2% to 4% by decade. Emergence of AAAs rises sharply in individuals aged  $\geq 60$  years old. It has also been consistently demonstrated that AAAs occur with greater frequency in men, smokers, and those with a family history of aortic aneurysm.

Data on prevalence of AAA varies between 1.3% and 12.5% in males, and between 0.0% and 5.2% in females. Overall prevalence varies from 4 to 8%.

Iliac artery aneurysms (IAAs) commonly occur concurrently with other more proximal arterial aneurysms. In contrast to generalized aorto-iliac aneurysms, isolated iliac aneurysms are prevalent in  $\leq 2\%$  of the general population.

Femoral artery true aneurysms are found predominantly in older men (70 years or older) and are associated with smoking and hypertension.

Popliteal artery aneurysms are rare in the general populations, although they are the most common peripheral artery aneurysms (70% of them). PAAs are exclusively found in men. A prevalence of around 1% in men has been reported in UK between 65 and 85 years.

### 4.3. Contra-indications

POLYMAILLE®C vascular prostheses are contraindicated for surgery of the thoracic aorta, coronary bypass, arteriovenous access, extracorporeal circulation and crossing the knee flexion crease.

POLYMAILLE®C vascular prostheses are contraindicated in patients with an immune reaction or hypersensitivity, known or suspected, to collagen of bovine origin.

---

PROTOCOL	2020-PMC-01
TITLE:	Safety and Performance of POLYMAILLE® C vascular prosthesis
EFFECTIVE DATE:	15 January 2021

---

## 5. STUDY DESIGN

POLYMAILLE® C is a retrospective, observational, multicentre, descriptive study which examine short and long-term outcomes of using POLYMAILLE® C. This study will be done on all comers Real World Data to collect clinical safety and performance data on the device.

### 5.1. Summary of relevant Clinical data

#### Prospective randomized clinical trial

*El-Barbary* (2014) conducted on its own initiative, a prospective randomized clinical trial with the aim to compare expanded polytetrafluoroethylene (ePTFE; 6-mm LifeSpan®) prosthesis and collagen-impregnated knitted polyester (Dacron; 6-mm POLYMAILLE® C) for above-knee (AK) femoro-popliteal bypass grafts in chronic ischemia patients. Between March 2010 and September 2012, 44 AK femoro-popliteal bypass grafts were randomly allocated to either an ePTFE (n=22) or a Dacron (n=22) vascular graft (6 mm in diameter). The median age was 62 (35-76) years for ePTFE group and 62 (39-69) years for Dacron group. The primary end point of the study was the primary patency at 6, 12 and 24 months. Secondary patency, amputation rate and complications were chosen as secondary endpoints.

Primary patency at 6, 12 and 24 months was 95%, 91% and 76% for PTFE and 95%, 95% and 86% for Dacron, respectively ( $p = 0.47$ ). Secondary patency at 6, 12 and 24 months was 95%, 95% and 86% for PTFE and 95%, 95% and 91% for Dacron, respectively ( $p = 0.77$ ).

Regarding safety, no deaths occurred within 30 days of surgery. Thirty-days complications occurred equally frequent in both groups. The following complications were reported in the Dacron group: 2 deaths (at 2 years), 1 deep wound infection, 1 major limb amputation, 3 minor amputations on toes or forefoot, 1 case of 30-day cardiac complications (myocardial infarction or arrhythmia). There was no significant difference in amputation, overall morbidity, or mortality rates between the two surgical graft populations, and the rate of limb salvage was not significantly different for the two graft materials. Results has also shown that the most significant predictors of early graft failure were diabetes mellitus and critical limb ischaemia.

This study showed that Dacron grafts may be at least as durable as ePTFE for above-knee bypass procedures, and might even be superior.

This study supports the use of knitted prosthetic grafts (POLYMAILLE® C) for the replacement of peripheral arteries during peripheral atherosclerotic arterial disease and collects the performance of vascular grafts (primary patency) up to 2 years of follow-up. This study also provides safety information.

#### Clinical survey (unpublished)

PEROUSE MEDICAL conducted a multicentre, non-prospective, non-comparative post-marking evaluation using evaluation questionnaires where the POLYMAILLE® C vascular graft was evaluated (NPCI 2009, Manufacturer's own report). The aim of this investigation was to evaluate the characteristics of the POLYMAILLE® C vascular graft by surgeons, in terms of comfort and ease of use

---

PROTOCOL	2020-PMC-01
TITLE:	Safety and Performance of POLYMAILLE® C vascular prosthesis
EFFECTIVE DATE:	15 January 2021

---

(suppleness, conformability, clean and safe cutting with scissors, ideal suturability, optimal circumferential stability).

From May 2008 to February 2009, 88 implanted POLYMAILLE® C vascular grafts have been included in this clinical survey. No inclusion or exclusion criteria were imposed. This clinical survey was conducted in 4 countries: Italia, Austria, Czech Republic and Belgium. There were no follow-up visits of implanted patients, as the aim of this survey was the assessment of the peri-operative prosthesis characteristics (before implantation, during implantation and after blood flow restoration).

As results from the questionnaire, it was concluded that: main interventions were elective (75%) with conventional surgery; interventions were conducted in the abdominal site or peripheral site (no thoracic use); bifurcated prosthesis was preferred (85.7%) for the abdominal site, while straight prosthesis was preferred (91.7%) for the peripheral site. This survey did not mention patient's data, therefore indication of prosthesis (aneurysmal or obliterative arteries) is not reported.

Surgeons considered the sensation (touch) of POLYMAILLE® C graft as excellent or good (97.7%), similarly to the suppleness (93.2%) and the ease of cutting (97.7%).

During the implantation, 94.3% considered the anastomotic conformability as excellent or good, similarly to the suturability (95.4%). Proximal anastomosis (both terminal and lateral) was easily performed as rated by 98.9% of the surgeons. Similarly, the distal anastomosis was considered easy to perform by 96.6% of the surgeons. The most frequent needles used in suture were round in both proximal and distal anastomosis (86.4% and 76.1% respectively). Comfort of POLYMAILLE® C vascular grafts was considered as excellent or good by 84.1% of surgeons (against 7.9% who considered the comfort as average or insufficient).

Difficulties during implantation were reported from one centre: leakage of graft beneath bifurcation, twisted markings of the graft, torsion of the graft in the canal of Hunter, bleeding of the graft.

After blood flow restoration: the general appearance was considered as excellent or good in 98.8% of cases; the limited circumferential dilatation and the longitudinal elongation were assessed as excellent or good (95.4% in both cases). Despite some cases of leakage of graft beneath bifurcation, torsion of the prosthesis in the canal of Hunter and bleeding of the graft, it was reported that the blood tightness of the graft was excellent or good in 95.5% of cases, and similar results were recorded for the blood tightness of the anastomoses (93.1%).

Regarding safety, among the 88 implanted patients, only 3 complications (3.4%) were reported during the intervention (1 bleeding, 1 cardiorespiratory failure leading to patient's death the day after, 1 operative re-anastomosis from external iliac to common femoral artery).

Following this NPCI evaluation questionnaire, it was concluded that POLYMAILLE® C was associated with high level of comfort and ease of use during conventional surgery. This clinical survey also supports the use of knitted prosthetic grafts for the replacement of abdominal and peripheral arteries. This clinical survey may be adapted to procedural success, however, it does not support long-term performance and safety of the prosthesis, as only peri-operative data were available.

This study supports the use of knitted prosthetic grafts (POLYMAILLE® C) for the replacement of abdominal and peripheral arteries and confirms the performance of vascular grafts (procedural success) in peri-operative period. This study also provides peri-operative safety information.

---

PROTOCOL	2020-PMC-01
TITLE:	Safety and Performance of POLYMAILLE® C vascular prosthesis
EFFECTIVE DATE:	15 January 2021

---

### **Vigilance data**

An ad hoc analysis of sales and complaints was obtained for the sixteen-year time period since January 2004. During that period more than 55 000 POLYMAILLE® C devices were sold. During the same time period a total of 37 complaints were reported yielding an overall complaint rate of 0.066% of POLYMAILLE® C (Manufacturer's data).

### **5.2. Rationale for PMCF study**

Available evidence confirms acceptability of performance and side effects related to POLYMAILLE® C; however intended claims on clinical safety and performance are not sufficiently supported with existing clinical evidence, especially for long term assessment and for abdominal surgical locations. In order to keep POLYMAILLE® C in European market, a post-market clinical follow-up (PMCF) study is needed.

### **5.3. Subjects**

The participating hospitals will screen all potential subjects and will select those who are appropriate for study inclusion, i.e. subjects implanted with POLYMAILLE® C for at least one year, or with complete data to death. As the study explores real world data, there is no exclusion criteria for subjects and all subjects with POLYMAILLE® C implanted for at least one year and up to 5 years will be included in the study.

All data will be retrieved from medical charts for each patient from time of surgery (considered as index date) until a maximum of 5 years after surgery.

Data from a minimum of 200 from 3 to 8 different sites in France will be evaluated. A minimum of 100 subjects will be evaluated for each main location of surgery (peripheral and abdominal).

Not more than 50% of study total enrolled subjects shall pertain to one unique centre.

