#### **5.3.2. Exclusion criteria**

Patients who have objected to the collect of their data.

---

PROTOCOL	2020-PMC-01
TITLE:	Safety and Performance of POLYMAILLE® C vascular prosthesis
EFFECTIVE DATE:	15 January 2021

---

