## 8. STATISTICAL CONSIDERATIONS

### 8.1. Statistical design, method and analytical procedures

All the patients participating in the study who met the eligibility criteria will be included in the study population.

A descriptive analysis with clinical characteristics of all patients included in the study will be performed at the index date.

Exploratory analyses will be conducted globally and by the 2 sub-populations. Results will be stratified according to 2 main surgical locations:

- Abdominal surgical location:
  - Aorto-aortic and/or aorto-iliac and/or aorto-femoral repair
- Peripheral surgical location:
  - Peripheral artery repair and extra anatomic bypasses

Since no hypotheses will be tested, study objectives will be addressed using descriptive statistics only. Given the real-world nature of the data, the use of multiple imputation methods for missing data would introduce bias as missing data cannot be considered completely at random (MCAR) or at random (MAR). Variables will not be imputed, with the exception of dates in which the exact day is missing: the missing day will be replaced by the middle day of the month.

Continuous variables will be described with number of patients with valid / missing observations, mean and its 95% confidence interval (95%CI), standard deviation (SD), median, 25 and 75 percentiles (P25 and P75, respectively), minimum and maximum. For non-normally distributed continuous variables geometric mean and its 95%CI will be reported too.

For categorical variables counts and percentages per category will be presented. Missing observations (including invalid observations) will be tabulated as a separate category. If the % of missing data does not exceed 10 %, the calculation of proportions will not include the missing/invalid category in the denominators.

P-values will be presented in the summary tables, in association with the descriptive statistics. In addition, 95% confidence intervals (95%CI) will be presented when considered convenient or relevant. Results will be graphically represented when appropriate to make interpretation easier.

The two-sided level of significance will be set at 0.05 for all the statistical tests performed.

Statistical calculations will be carried out by using R software. More details on the statistical analysis will be provided in the Statistical Analysis Plan.

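### The 50% centre cap conflicts with including every eligible subject whenever one centre holds more than half of them, and no rule says who is then left out

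*Protocol*

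**What the plan says.** Three statements in Protocol section 5.3 bear on who enters the study.

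- Inclusion is unconditional: "all subjects with POLYMAILLE® C implanted for at least one year and up to 5 years will be included in the study".
- One centre's share is limited: "Not more than 50% of study total enrolled subjects shall pertain to one unique centre".
- Size and spread are set: "Data from a minimum of 200 from 3 to 8 different sites in France will be evaluated", with at least 100 subjects for each of the two surgical locations.

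Section 5.3 also gives the hospitals the task of screening all potential subjects and selecting the appropriate ones. It defines these as subjects implanted for at least one year or with complete data to death.

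Two other sections could have dealt with a centre above the cap, but do not. Section 5.3.2 has a single exclusion: "Patients who have objected to the collect of their data". Section 8.1 defines the analysis set without reference to centre share: "All the patients participating in the study who met the eligibility criteria will be included in the study population". No section gives an order of inclusion (consecutive, by date or random) or says what happens when a centre passes half of the total.

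**The concern.** An all-comers rule and a cap on one centre's share are each reasonable. Together they need a third rule, for the case where following the first breaks the second. Without it, eligible patients have to be left out on grounds that the protocol does not state.

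This matters more in a retrospective study than in a prospective one. Patency, reintervention and death are already recorded in the chart when inclusion is decided. An omission with no stated rule can therefore depend on outcome, even unintentionally, and both primary endpoints (primary patency at 1 year, mortality at 30 days) are exposed to it. The cap is also a share of the total enrolled, which is known only once every site has reported. Any trimming would thus tend to come late, possibly after abstraction.

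The second consequence is for size. Section 8.2 bases the number of patients on what the hospitals can realistically supply and states no margin above 200. Patients removed to satisfy the cap could take the study below its own minimum.

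**Working it through.** **Plan's own figure.** The sample size has no formula. Its only arithmetic is 100 abdominal + 100 peripheral = 200, which agrees with the stated minimum.

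**Inputs from the protocol.** Cap of 50% of total enrolled; all eligible subjects included; 3 to 8 sites; minimum 200, with 100 per location (all section 5.3).

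**Assumed inputs.** Site volumes and patency rates, because the protocol gives neither.

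**Step 1: when the rules conflict.** Let d be the eligible number at the largest centre and o the number at all other centres together. The cap requires d/(d + o) ≤ 0.5, which is the same as d ≤ o.

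- If d ≤ o, nobody is left out and both rules hold.
- If d > o, the largest centre can contribute only o subjects. The number left out is d − o and the final total is 2 × o.
- For 2 × o to reach 200, the other centres must supply o ≥ 100.

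**Step 2: size of the omission for assumed centre shares.**

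| Eligible | Largest centre's share | d | o | Left out (d − o) | Final N (2 × o when d ≥ o) |
|---|---|---|---|---|---|
| 250 | 50% | 125 | 125 | 0 | 250 |
| 250 | 55% | 138 | 112 | 26 | 224 |
| 250 | 60% | 150 | 100 | 50 | 200 |
| 250 | 70% | 175 | 75 | 100 | 150 |
| 200 | 55% | 110 | 90 | 20 | 180 |
| 200 | 60% | 120 | 80 | 40 | 160 |
| 200 | 70% | 140 | 60 | 80 | 120 |

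With exactly 200 eligible, any share above half takes the total below 200. With 250 eligible, the total stays at or above 200 up to a 60% share.

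**Step 3: how far one-year patency could move, three sites.** Assume 140, 40 and 40 eligible (220 in all) and true patency of 90% at each site. Failures are then 14 + 4 + 4 = 22, and full inclusion gives (220 − 22)/220 = 90%.

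- Cap: d = 140, o = 80. The large site keeps 80 and omits 60 (60/140 = 43%). Final N = 160.
- All 14 of its failures omitted: 8 failures remain, (160 − 8)/160 = 95%.
- None of its failures omitted: 22 failures remain, (160 − 22)/160 = 86.25%.
- 60 omitted at random: 8 failures expected among the 80 kept, (160 − 16)/160 = 90%.

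**Step 4: the same check with the minimum still met.** Assume 150 eligible at the largest centre and 100 elsewhere, so 50 are left out and N = 200. At 90% patency there are 15 + 10 failures. The reported figure can lie anywhere from (200 − 25)/200 = 87.5% to (200 − 10)/200 = 95.0%. With true patency of about 85% the bounds are 81.0% and 92.5%; with about 95% they are 93.5% and 97.5%.

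The limits in steps 3 and 4 are what free choice of the omitted patients could produce at the extreme. They are not expected bias.

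**The case against.** The strongest reply is that the cap may never bind. With up to eight sites, no centre need hold more than half of the eligible subjects. The cap can also be read as a constraint on site mix, met by opening further sites within the permitted range and leaving nobody out. Section 8.2 indicates that hospital volumes were considered in planning. This stands as far as it goes: the conflict is conditional, and a reader who infers that the two rules can never hold together goes beyond the text. However, the protocol does not name added sites as the remedy. The number of sites stops at eight, and the Synopsis allows six months for data collection.

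A reader might also infer from "The participating hospitals will screen all potential subjects and will select those who are appropriate for study inclusion" that a dominant site would choose which patients count. The documents do not support that. The sentence goes on to define appropriate subjects by objective criteria, and no section describes selection by outcome. Section 13 also has data collection begin only after eligible patients have been informed and have not objected. What remains is that eligibility criteria cannot settle which of several eligible patients to leave out. Nor are sites unaware of outcome at that stage, since section 5.3.1 makes eligibility depend on one-year follow-up data or complete data to death.

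It can be said that 200 is a commitment, so a total of 160 would prompt action and would not simply be accepted. That is fair, but the action is not specified.

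Finally, this might be thought a matter for the statistical analysis plan. Who enters the study is decided before analysis, and an analysis plan cannot undo a selection made when charts are abstracted.

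**Conclusion.** The point holds in conditional form. Two entry rules in section 5.3 conflict whenever one centre has more eligible subjects than all the others combined, and the protocol has no rule for who is then left out. Whether that situation arises cannot be judged from the protocol.

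If it arises, d − o patients are omitted and the total becomes 2 × o, which is below 200 unless the other centres supply at least 100. On assumed sites of 140, 40 and 40 with 90% patency at each, the worst case in the favourable direction is 95% reported on 160 subjects. That requires every one of the large site's 14 failures to be among the 60 omitted, so it is a bound and not a forecast. Random omission leaves the expected figure at 90% when the sites share the same patency. If sites differ, the cap itself changes their weights, whichever patients are omitted. The same mechanism applies to 30-day mortality, but the protocol offers no rate from which to size it.

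This is more than missing detail, because two stated rules can collide where outcomes are already known. It is a contingency to be closed, not a demonstrated bias.

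**What to change.** Amend section 5.3 as follows.

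1. Each site lists all eligible implants by date of surgery before outcomes are abstracted.
2. The cap is checked once, when all site lists are complete and objections are known, because it is a share of a total that is not fixed earlier.
3. If a centre exceeds the cap, the patients left out are chosen by a prespecified outcome-blind rule. One example is a random draw from that centre's list, stratified proportionately by surgical location and year of surgery. Stratifying by year keeps the longer-followed implants represented, which matters because section 5.2 names long-term evidence as a gap. Counting back from a recent date would drop those implants first.
4. The number eligible but not included is reported for each site.
5. The sentence on including all subjects is made subject to this rule. If adding sites is the intended response to a dominant centre or a total below 200, the section should say so.

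The cost is a few sentences, a dated implant list per site before abstraction, and a per-site count in the report. The drawback is timing: the cap can be applied only after the last list is in, which uses part of the six-month collection period.
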